Protocol Title: Addressing Cervical Cancer Disparity in South Florida: CBPR in Action Version Date: 2/4/16 NCT#02202109

- 1) **Protocol Title** Addressing Cervical Cancer Disparity in South Florida: CBPR in Action
- 2) **Principal Investigator** [name], MPH
- 3) **Sub-investigator** [name], MPH
- 4) **Study Contact** [name], MBA
- 5) Study Personnel (Listed on IRB7)
- 6) **IRB Review History**

N/A

7) **Objectives**

The study entitled "Health in Your Hands" will test the significance of community health worker participation by comparing Human Papilloma Virus (HPV) self-sampling provided by a community health worker and HPV self-sampling provided by mail. The study will enroll 700 participants in communities characterized by health disparities and lack of access to the formal healthcare system, such as Little Haiti, Hialeah, and South Dade.

8) Background*

In Miami, Florida, cervical cancer is a particular problem for Haitian and Caribbean Hispanic women. When compared to other racial/ethnic minority and immigrant groups in the Miami metropolitan area, Haitian and Hispanic women contribute disproportionately to cervical cancer incidence, morbidity and mortality, largely as a function of their underutilization of Pap smear screening. They do not undergo Pap smear screening for a myriad of reasons, including, but not limited to: poverty; language difficulties; limited access to health care; lack of knowledge about cancer and the importance of early detection; cancer fatalism or the belief that cancer implies death; and, cultural norms about health and disease prevention. The proposed project aims to overcome such barriers.

With funding from the National Cancer Institute, we have documented the prevalence of lifetime and routine Pap smear among women living in our communities of interest. Between March and May 2011, the community health workers approached approximately 200 women from various community venues across Little Haiti, Hialeah and West Perrine including Laundromats, health clinics, and churches. Of the participants, 71% reported having at least one Pap smear in their life. Of those with a history of screening (n=143), only 80% reported having a least one Pap smear in the past three years as recommended by national guidelines. There is not a direct comparison for our data, though in relation to national averages and data, the women in our sample appear to be under-screened.

Following this data, a pilot study was conducted (funded by UM Sylvester and the University of Miami Institute for Women's Health) to examine whether Haitian women consider self-sampling a culturally-acceptable alternative to the Pap smear. A total of 250 women agreed to participate in

the study, which involved cervical self-sampling with the POI/NIH device (essentially a long q-tip with a protective sheath), as well as, completing a detailed survey. Findings indicate that acceptability of the device is high, that the majority of women prefer the self-sampler to the traditional, physician speculum exam and find it easy and comfortable to use. In addition to such positive results, this pilot study helped to establish the infrastructure necessary for successfully carrying out the proposed study.

9) Inclusion and Exclusion Criteria

Rational for inclusion/exclusion criteria: our target population is ethnic minority females aged 30-65 living in one of the three target communities who have not been screened for cervical cancer in the past three years (as per recent guidelines).

To be eligible women must be:

- Haitian, Hispanic, or African American
- ages 30-65 years
- report not having had a pap smear in the last three years
- live in the cities of Miami/Little Haiti, Hialeah or unincorporated Southern Miami-Dade

EXCLUSION CRITERIA:

Women will not be included in the study if they:

- report having had a hysterectomy
- have a history of cervical cancer
- plan to move outside of Miami-Dade county during the next six months
- are enrolled in any other cancer prevention/outreach related study

The study will exclude:

- Adults unable to consent
- Individuals who are not yet adults (infants, children, teenagers)
- Pregnant women
- Prisoners

10) Number of Subjects

700

11) Study-Wide Recruitment Methods

Participants will be recruited to participate in the study primarily through the efforts of Community Health Workers (CHWs), who are indigenous to the area, employed by our community partners and certified to conduct research by the University of Miami (UM) Institutional Review Board (IRB). The CHWs are not UM employees but are CITI-certified and are from either the Health

Choice Network, which includes the Citrus Health Network and Community Health of South Florida, Inc. (CHI), and the Center for Haitian Studies (CHS).

The CHWs will be trained by the Principal Investigator and community partners about how to approach potentially eligible individuals and encourage their participation in the study. They will recruit participants from various community settings in Little Haiti, Hialeah, and South Dade, such as laundromats, flea markets, health clinics, local botanicas, and church gatherings, that have been identified through ethnographic community mapping as regularly frequented by the target population. The CHWs will also rely heavily on their own social networks and those of the community leaders, to identify potentially eligible participants.

Although we recognize the inherent limitations in such non-probability approaches to sampling, our preliminary research in Little Haiti and Hialeah indicates that more random recruitment strategies engender suspicion and compromise overall participation. As a result, we must employ a non-probability, purposive quota-based sampling strategy to recruit participants. However, we will attempt to introduce randomness into this sample by using recruitment protocols that direct the CHWs to approach every Nth woman in socially salient community settings. We will compare study samples with data abstracted from the US census to better understand whether our sample is, in fact, representative of our target communities.

Community Advisory Group members will also promote our research agenda through culturallyappropriate communication channels, such as radio and print media. Radio is the primary news source for a majority of residents in our target communities, and can help generate community interest in, and support for the proposed research.

12) Study Timelines

An individual will participate in the study for six months (baseline interview at intake and a sixmonth follow-up interview). We estimate the time necessary to enroll all study subjects will be 27 months. The estimated date for completion of the study is May 1, 2017.

13) Study Endpoints*

Our primary endpoint is a returned HPV self-sampler kit. We have several planned subgroup analysis to help us understand if our intervention was more effective among certain population sub-groups. We therefore propose to examine whether the intervention was more efficacious among women with lower levels of educational attainment and those who are uninsured/underinsured. We consider all these analysis to be hypothesis generating, rather than hypothesis testing, given limited power. We also plan to examine several secondary endpoints, including: a) Access to care (health insurance, having a usual source of care, and visit to provider in six months). These would be analyzed as binary variables and would help explore if HPV self-sampling led to a decrease in access. b) Cervical cancer knowledge to help determine study fidelity. This is a continuous variable based on summed number of correct answers. c) Knowledge of test results and, for those with an abnormal screen, the proportion of women in each group who received appropriate initial follow-up within 30 days of the abnormal screen d) Acceptability of screening delivery.

14) **Procedures Involved***

Determination of eligibility The CHWs will screen potential participants for eligibility by asking whether they are 1) Haitian, Hispanic or African American, 2) 30-65 years of age or older, 3) have not had a Pap smear in the past three years, 4) has not had a hysterectomy, 5) has not been enrolled in a similar study (e.g. SUCCESS), 6) is not pregnant, 7) will not move in the next 6 months. For those women who screen potentially eligible, the CHW will further describe the study. Potential participants will be told that we are conducting a research study to determine the best method to increase rates of cervical cancer screening among women in their community. They will be told that the study will involve a brief education session about cervical cancer prevention and treatment, as well as instructions on how to use the HPV self-sampler we will be providing them with.

- Women who decline participation: For women who are potentially eligible but were not interested in participating, the brief demographic information collected during the eligibility screen (age, ethnicity) will be kept without any identifiable information. This data will be used to compare responders versus non-responders.
- Women who agree to participate: The CHW will obtain signed informed consent from the women who are interested in participating.

Informed Consent and Intake Survey: After obtaining consent, the CHW will proceed with the intake interview. The intake interview will be conducted by our research assistants/community health educators (CHEs) to avoid introducing bias into our study design. Prior to beginning the intake survey, the CHE will first conduct another inclusion screen to verify that the potential participant still meets study inclusion criteria. The CHE will then re-explain the study to the potential participant and answer any questions she may have. If she is still agreeable to participating, the CHE will obtain signed informed consent. After obtaining consent, the CHE will proceed with the intake interview. The CHW will explain to participant that she will participate in two interviews 6 months apart, where each interview will take approximately 30 minutes to complete. This home interview will be conducted using laptop computers with wireless cards allowing access to the Research Electronic Data Capture (REDCap) web-based platform (see below). Backup paper copies will be available in case the CHE experiences difficulty accessing the web.

After completion of the intake survey, the participant will receive a \$25 gift card for their time and participation.

Randomization: Once participants complete the screening intake, they will be randomized into one of two possible interventions. Participants will be provided randomization information via phone by the CHW. Randomization will be done by REDCap, a secure web-based and HIPPA compliant system that allows to manage online surveys, database and reporting.

A custom allocation list has been created, which serves as a lookup table for deciding how to randomize subjects. Randomization of subjects will occur on the data collection form where your randomization field. After a subject has been randomized, it will become permanently locked and unmodifiable. The randomization field will always be locked and unmodifiable both before and after randomization has occurred for a subject. When the user randomizes the subject, REDCap will check the allocation table and assign that subject's randomization field value, which will be derived from the next match in the table based upon the criteria. In this case, it will simply provide the subject with the very next value in the allocation table.

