The CHWs will identify and recruit potential subjects at various community venues that they deem appropriate and at which women tend to congregate. These may include, but are not limited to laundromats, churches, health clinics, and flea markets in Little Haiti, Hialeah, and South Dade.

Mailed specimens will be taken to the Oncogenomic Core Facility at UM Sylvester Comprehensive Cancer Center (SCCC) for high-risk HPV detection and HPV viral genotyping.

24) **Resources Available**

The current research study uses SUCCESS' infrastructure to accomplish study aims and build necessary capacity to support future large scale, community-based interventions to address other areas of cancer disparity. SUCCESS has established Community Advisory Groups (CAGs) in Little Haiti and a steering Community Leadership Board (CLB). The CLB involves representation from members of all CAGs as well as other local experts in cancer prevention and control. The CLB meets quarterly to maximize information exchange between CAGs and also to ensure that key findings are disseminated to the community in a timely and appropriate manner. Additionally, SUCCESS is an active member of the Southeast Florida Cancer Control Collaborative, a group of more than 50 local organizations that collaborate on cancer prevention, education, and patient services, and may provide future opportunities for dissemination and expansion of the pilot intervention.

25) **Confidentiality**

Multiple steps will be taken to guarantee confidentiality. All paper-based surveys and forms will be entered and uploaded using Research Electronic Data Capture (REDCap). All REDCap data is securely hosted by the University of Miami's IT Department. Research IT administers project creation, user account management, and movement of projects from development to production. Authentication is performed via CaneID Authentication Service (CAS), the same institution-wide system used for a variety of applications such as myUM. Other electronic data will be stored in

password-protected files that only [name] and the Study Manager and study staff will be able to access. There are multiple levels of security once placed on the local network. Paper copies will similarly be stored in a locked file drawer that only Study Manager and the Data Manager will be able to access.

All study personnel will be certified to conduct human subjects' research by the University of Miami Institutional Review Board.

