Protocol Title: Addressing Cervical Cancer Disparity in South Florida: CBPR in Action Version Date: 2/2/17 NCT#02202109

Statistical Analysis

Baseline characteristics were compared across the two study arms using chi-square tests (categorical data) and t-tests (continuous data). Crude differences in proportion of women screened by study arm (overall and stratified by neighborhood site) were tested using chi-square tests. We then modeled the association between sociodemographic variables and screening completion using univariate and multivariable logistic regression analyses. We included neighborhood site, age, income, insurance status, education, Pap history, marital status and citizenship status as covariates in the multivariable analysis. Race/ethnicity was not analyzed as it was highly collinear with site (e.g. all Haitians resided in Little Haiti). We report odds ratios (ORs) and corresponding 95% confidence intervals (CI) for the regression analyses. Secondary outcomes were analyzed using paired McNemar chi-square tests for the overall sample, and stratified by neighborhood site. All statistical tests were two-sided, with significance set at the p < 0.05 level. The data were analyzed using SAS 9.4 (SAS Institute Inc., Cary, NC, USA).

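### Recruiting some women at health clinics can inflate their intake answer on provider visits and bias the pooled before-after test of that item downward

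*Protocol*

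**What the plan says.** Protocol Section 11 (Study-Wide Recruitment Methods) has community health workers (CHWs) approach women in settings "such as laundromats, flea markets, health clinics, local botanicas, and church gatherings". It adds a second route: "The CHWs will also rely heavily on their own social networks and those of the community leaders, to identify potentially eligible participants". Section 23 (Setting) repeats the venues more loosely: "These may include, but are not limited to laundromats, churches, health clinics, and flea markets in Little Haiti, Hialeah, and South Dade". Neither section gives a clinic quota or share.

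Section 13 (Study Endpoints) lists access to care as a secondary endpoint with three items: "health insurance, having a usual source of care, and visit to provider in six months". It states their purpose: "These would be analyzed as binary variables and would help explore if HPV self-sampling led to a decrease in access".

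The SAP gives one analysis for this class of outcome: "Secondary outcomes were analyzed using paired McNemar chi-square tests for the overall sample, and stratified by neighborhood site". It adds: "All statistical tests were two-sided, with significance set at the p < 0.05 level". It states no between-arm test for secondary outcomes. Sections 12 and 14 place the two interviews at intake and at six months, with intake done at home after recruitment.

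Neither document mentions recording the recruitment venue, using it in the analysis, or removing the recruitment visit from the intake answer. Section 11 acknowledges the limits of non-probability sampling in general and plans a census comparison. That comparison addresses representativeness, not this endpoint.

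**The concern.** A woman recruited at a clinic has been selected, at least in part, on the quantity that the provider-visit item measures. If the item looks back over recent months and counts that visit, she tends to answer yes at intake. At exit she is no longer selected in that way, and some such women will answer no although nothing in their access has changed. This is regression to the mean caused by selection on the outcome at baseline.

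A paired test of intake against exit in the pooled sample cannot separate this drop from an effect of self-sampling. Randomisation gives no protection, because the stated test does not compare the arms. At stake is the reading of one access item whose purpose is to pick up a possible harm: the test could signal a fall that did not happen, or understate a rise that did.

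**Working it through.** The documents give no figure to reproduce on this point. They state no clinic share, baseline visit rate, within-woman correlation or power for the McNemar test.

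**Inputs from the documents**
- 700 women (Protocol Sections 7 and 10), taken as 700 complete pairs.
- Two-sided 0.05 (SAP), so a 2.5% nominal chance of a significant fall when nothing changes.

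**Assumptions**
- A share q is recruited at clinics. These women answer yes at intake, and yes at exit with probability v.
- The other women have a steady visit rate of p = 0.5 and an intake-exit correlation of 0.4. Their chance of changing in either direction is p(1 − p)(1 − 0.4) = 0.25 × 0.6 = 0.15 each way.

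**Formulas**
- Spurious change = −q(1 − v).
- Expected yes-to-no pairs: b = n[q(1 − v) + 0.15(1 − q)]. Expected no-to-yes pairs: c = n × 0.15(1 − q).
- With d = b − c and s = b + c, the chance of a significant fall is about Φ[(d − 1.96√s)/√(s − d²/n)].

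**Worked case, q = 10%, v = 0.5**
- b = 700 × (0.05 + 0.135) = 129.5; c = 700 × 0.135 = 94.5; d = 35; s = 224.
- (35 − 1.96 × 14.97)/√(224 − 1.75) = 5.67/14.91 = 0.38, and Φ(0.38) = 65%.

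**Other settings** (4,000 simulated trials each; a repeat run agreed within about two points)

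| Clinic share q | v = 0.5: change, chance of significant fall | v = 0.7: change, chance of significant fall |
|---|---|---|
| 5% | −2.5 points, 23% | −1.5 points, 10% |
| 10% | −5 points, 65% | −3 points, 30% |
| 20% | −10 points, over 99% | −6 points, 84% |

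With 560 pairs, q = 10% and v = 0.5, the chance is still 57%.

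**Not every clinic recruit answers yes.** Suppose 70% do because of the visit and the rest behave like other women. At q = 10% the affected share is 7%.
- v = 0.7: b = 700 × (0.07 × 0.3 + 0.93 × 0.15) = 112.35; c = 97.65; d = 14.7; s = 210. Then (14.7 − 28.40)/14.48 = −0.95, and Φ(−0.95) = 17%.
- v = 0.5: 36% in simulation (38% by the formula).

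**A second parameterisation.** Clinic recruits answer yes at exit with probability p + ρ(1 − p), so the artefactual fall is q(1 − p)(1 − ρ). With p = 0.5, ρ = 0.2 and q = 10%, the fall is 0.10 × 0.5 × 0.8 = 4.0 points and the chance 39%. Over p = 0.3 to 0.7 and ρ = 0.2 to 0.5, the chance at a 10% share runs from 14% to 70%.

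**Offset from study-prompted visits.** Return to the first model with q = 10% and v = 0.5, all clinic recruits answering yes at intake.
- Intake rate: 0.10 × 1 + 0.90 × 0.5 = 55%.
- Exit rate without any prompting: 0.10 × 0.5 + 0.90 × 0.5 = 50%.
- If study contact turns 10% of exit no answers into yes, the exit rate is 0.50 + 0.10 × 0.50 = 55%.

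The net change is zero and a significant fall appears in about 3% of trials, close to nominal. A real 5-point rise has been hidden. In the second model the same offset cuts the central chance from 39% to 1.0%.

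**The case against.** The strongest reply is that the premise is partly inferred. The questionnaire is not in the documents, so the intake wording and look-back window are unknown. That the item is asked at intake follows only from the paired test, and the SAP does not name the outcomes that test covers. Clinics are one of five example venues beside heavy use of personal networks, and nothing points to a large share. A woman at a clinic may be accompanying someone. All of this stands. It makes the size conditional, but it does not remove the bias if the recruitment visit is counted.

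A reader might infer that the plan will report a false fall in access. The documents do not support that. Under Section 14, HPV-positive women are navigated to care, HPV-negative women are encouraged to see their doctor, and every kit carries information on partner services. The eligibility rule of no Pap smear in three years may also select low users, whose visits could drift upward. The net direction is therefore not established. The recruitment artefact is still subtracted from whatever real change occurs.

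It can also be argued that the root problem is the lack of a between-arm test. Such a test is immune to this artefact: with 350 women per arm, simulated error rates were 5.4%, 5.2% and 5.8% at clinic shares of 0%, 10% and 30%. It would be a useful addition, but both arms receive self-sampling, so it cannot answer the question that Section 13 asks.

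**Conclusion.** The point holds in conditional form. If the intake item counts the visit at which a woman was found, the pooled paired test of provider visits is biased downward. With 700 pairs, no true change and a 10% clinic share, a significant false fall occurs in roughly 17% to 65% of trials under the main assumptions, against a nominal 2.5%. Study-prompted visits may cancel this, in which case the harm is a hidden rise.

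The finding covers the provider-visit item only. A reader might extend it to usual source of care, to insurance or to false differences between sites. The documents do not support this: the first two are standing arrangements with no shown reason to lapse by exit, and nothing indicates how the clinic share varies by site. The primary endpoint, return of the kit, is not shown to be affected.

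**What to change.** 1. Record venue type (clinic or not) for each woman at the Section 14 eligibility screen.
2. Word the intake provider-visit item to exclude the visit at which she was recruited, over the same six-month window as at exit. If a woman's visit rate is steady, the periods before and after the recruitment visit are then equally likely to contain another visit, even if clinic recruits are heavy users.
3. In the SAP, keep the paired test in all women, repeat it without clinic-recruited women as a sensitivity analysis, and state that a before-after fall will not be attributed to self-sampling if it disappears there.

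The SAP is dated 2/2/17 and written in the past tense, so the forms may no longer be open to change. In that case venue should be taken from recruitment records, or the limitation stated if no such records exist.

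The cost is one extra field, one clause in the questionnaire and one SAP sentence. The sensitivity analysis is less precise: at a 10% clinic share it would use 630 of 700 pairs.

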The HPV self-sampler kit will include: 1) the HPV self-sampler (collection swab and the vial for collecting and storing the specimen; 2) a pre-addressed, stamped envelope for returning the vial to the SCCC laboratory for testing; 3) a postcard which includes a picture and information of the CHW that serves to re-orient the participant to the focus of the study; 4) an instructional sheet that visually depicts the steps for self-sampling; 5) information provided by our community partner in each site about their organization, the medical services provided, and how to schedule a Pap smear. We believe it is necessary for women to be exposed to information about Pap smears, given that they remain the standard for disease prevention throughout the life course. At the sixmonth follow-up interview, participants in this arm will be asked for detailed feedback about the kit and any recommendations for how to improve it.

The CHW will call participants within a week, using the randomization phone script, to inform them of 1) randomization group allocation, 2) conduct brief health education over the phone, and 3) schedule a home visit (Group 1) or inform participant that kit will be mailed within one week (Group 2).

Within one week after completing the intake interview, women randomized to the intervention arm will receive a HPV self-sampling kit via mail (intervention arm- Group 2) or will be given a self-sampling kit by the CHW (control arm- Group 1).

Group 1: Control Group (CHW) - Participants receive HPV self-sampler at **home visit:** . During the home visit, the CHW will provide the participant with brief health education and offer the HPV self-sampler accompanied by an instruction sheet on how to use the self-sampler. The education will include: 1) health education on the importance of cervical cancer screening using a short intervention/educational script and 2) motivation to encourage women to have screening using the HPV self-sampler. Women will also be informed of the following: 1) HPV infection usually is not detectable or harmful; 2) nearly everyone who has had sexual intercourse has been exposed to HPV and infection is very common; 3) a positive HPV test result does not indicate the presence of cancer and that not all women who test positive for an HPV infection will not develop advanced

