cancer. It will also be stressed to women that if they have not seen a doctor recently they will still need to see a provider to address other health issues, which may include a gynecologic exam. They will also be advised that if HPV obtained through self-sampling is positive, they will need follow-up medical care at our clinical sites. The participant will have the option of self-sampling at home or mailing the kit back.

Group 2: Intervention Group (Mail Self-Sampler Kit): Participants receive the kit via mail. The Study Manager mails the self-sampler kit to the participant. The CHW will also provide the participant with brief education via phone utilizing a short intervention/educational script. The participant will follow instructions on instruction sheet provided in the kit, and once self-sampling is completed, participant will mail the kit to UM/SCCC.

Report of HPV Lab Results

The Study Manager will receive test results from lab and provide information to CHWs. CHWs will call participants within 4-6 weeks to notify them of their test results when they are received. Participants who test negative will be encouraged to follow-up with their doctor and rescreen in 36 months, based on the US Preventive Services Task Force (USPSTF) guidelines. Participants whose test results indicate insufficient sample (insufficient cellular quantity for analysis) would be asked if they had a hysterectomy. If no, the participant will provide a second sample, and an appointment will be scheduled by CHW. If answered yes, the HPV lab result will be reported to the Study Manager. Participants who test positive for HPV will be navigated to appropriate follow-up care with our community partners and/or Jackson Memorial Hospital (JMH) within 30 days of receiving the result. JMH is the safety net hospital for Miami-Dade County and provides free and low cost care to indigent and medically underserved individuals in the Miami metropolitan area. The CHWs will work with JMH staff to ensure that women with abnormal findings receive timely follow up. The CHWs will follow up with participants who do not return the kit within 30 days.

At 4 months, the CHW calls participants in both arms to verify contact information only.

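### The access-to-care endpoint asks whether self-sampling reduced access, but both arms self-sample and the planned paired test has no comparator, so the trial cannot estimate that effect

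*Protocol*

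**What the plan says.** Protocol Section 13 lists access to care as secondary endpoint (a), made up of three binary items: "health insurance, having a usual source of care, and visit to provider in six months". Its stated purpose is that these "would help explore if HPV self-sampling led to a decrease in access".

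Section 7 sets the randomised comparison as "HPV) self-sampling provided by a community health worker and HPV self-sampling provided by mail". Section 14 gives a kit to both groups within a week of intake, by post or from the community health worker (CHW), and offers self-sampling to both arms again at exit. No woman is assigned to an arm without it.

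Section 14 also promotes contact with providers during follow-up:
- After a positive result: "Participants who test positive for HPV will be navigated to appropriate follow-up care", within 30 days of the result.
- After a negative result: "Participants who test negative will be encouraged to follow-up with their doctor".
- At the Group 1 home visit, women who have not recently seen a doctor are told "they will still need to see a provider to address other health issues".
- Every kit carries partner-clinic information that covers "the medical services provided, and how to schedule a Pap smear".

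The SAP analyses secondary outcomes by paired McNemar tests, for the whole sample and by neighbourhood site, two-sided at 0.05. It describes no comparison of secondary outcomes between arms.

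**The concern.** The purpose given for endpoint (a) is causal and concerns self-sampling itself. Answering it needs women who were not offered self-sampling, and the trial has none. If self-sampling lowered access equally in both arms, the arm contrast would show nothing. A before-after change mixes any effect of self-sampling with time trends, CHW education and study navigation.

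The provider-visit item has a further problem. The protocol itself generates or prompts visits inside the six-month window, so the observed rate can stay flat or rise while routine care falls. That bias works against seeing the decrease the endpoint is there to explore, so the likelier error is false reassurance.

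**Working it through.** The documents give no figure for this endpoint, so there is nothing to reproduce. The main point is structural; the calculations below only illustrate its size. The 700 comes from Section 10. All rates, 1:1 allocation (350 per arm) and complete follow-up are assumptions.

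**1. What each available contrast estimates.**
- Home visit versus mail at six months: the effect of delivery mode, because both sides self-sample.
- Intake versus exit, pooled over arms (the natural reading of a paired McNemar test here, since women are not matched across arms): net change over six months from all causes.
- Neither is the effect of self-sampling compared with none.

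**2. The arm contrast when self-sampling does reduce visits.** Suppose visits fall from 50% to 40% in both arms. The expected arm difference is 40% - 40% = 0, and the two-proportion test rejects 5.0% of the time, which is alpha. Suppose instead that the 10-point fall occurs only in women who use the kit. Uptake gaps of 5, 10 and 20 points, starting from 70% uptake, then give arm differences of 0.5, 1 and 2 points, with power of 5.2%, 5.8% and 8.3%. A difference in uptake does not rescue the question.

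**3. Share of women with a navigated visit (h).** h = kit return x HPV positive x attendance.
- Low: 0.70 x 0.10 x 0.80 = 0.056, or 39 of 700.
- High: 0.90 x 0.25 x 0.80 = 0.18, or 126 of 700.

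**4. Fall in routine visits that is fully hidden.** Let p0 be the baseline visit rate and d the true fall. If navigated visits are independent of other care, the observed rate is (p0 - d) + [1 - (p0 - d)] x h. Setting this equal to p0 gives d = h(1 - p0)/(1 - h).

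| p0 | h = 5.6% | h = 18% |
|---|---|---|
| 30% | 0.056 x 0.7/0.944 = 4.2 points | 0.18 x 0.7/0.82 = 15.4 points |
| 50% | 0.056 x 0.5/0.944 = 3.0 points | 0.18 x 0.5/0.82 = 11.0 points |
| 70% | 0.056 x 0.3/0.944 = 1.8 points | 0.18 x 0.3/0.82 = 6.6 points |

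Only navigated visits are counted here. Visits prompted by the advice to HPV-negative women, the home-visit education or the kit insert would add to them.

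**5. Effect on the planned test.** Simulated McNemar test, 700 pairs, 50% baseline, assumed latent within-woman correlation 0.4, 3,000 runs:

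| True fall | h | Significant fall | Significant rise |
|---|---|---|---|
| 5 points | 0 | 61% | 0% |
| 5 points | 8% | 4% | 1% |
| 5 points | 12.8% | 0.2% | 14% |
| 10 points | 0 | 99% | 0% |
| 10 points | 8% | 60% | 0% |
| 10 points | 12.8% | 16% | 0.2% |

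**The case against.** The strongest defence is that the protocol promises only to help explore the question, for one secondary endpoint, so a causal phrase is a small wording fault. The modest wording is a fair point, but an exploratory label does not supply a comparator, and the SAP adds no analysis that would.

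It can also be said that endpoint (c) already reports, by group, timely initial follow-up after an abnormal screen. So much of the navigated care is measured separately and can be read beside (a). That stands, but it does not take those visits out of the provider-visit item.

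Some stronger readings are tempting but not supported:

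- **That navigated visits contaminate the arm contrast.** If one arm returns more kits, finds more positives and so has more visits, that chain is a pathway by which delivery mode acts. It belongs in a comparison by delivery mode.
- **That navigated visits should be scored out.** Doing so conditions on kit return and test result, both of which follow randomisation. A woman who would have seen a provider anyway, but whose visit was the navigated one, would count as having none.
- **That a fall of 5.6 to 18 points could be hidden.** This is a ceiling, reached only if every navigated visit goes to a woman with no other visit. The item is binary, so navigation adds nothing for a woman who already had one. Late kit returns, including those after the exit re-offer, and loss to follow-up would reduce it further.
- **That visits would drift upward because of who was enrolled.** Eligibility is based on Pap history, not provider visits, and recruitment venues include health clinics. The documents give no basis for an expected rise.

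**Conclusion.** The concern holds. As written, the purpose of endpoint (a) cannot be met by the randomised contrast or by the planned paired test, and this applies to all three items. It does not depend on any assumed rate.

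Masking is narrower. It applies directly to provider visits, plausibly to usual source of care through linkage with partner clinics, and not directly to insurance. With 70-90% kit return, 10-25% HPV positive, 80% attendance and independence from other care, the fully hidden fall is about 3.0 to 11.0 points at a 50% baseline and 1.8 to 6.6 at 70%. These figures show what is possible; they do not predict what happened.

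A reader might infer that the trial plans to declare self-sampling harmless to access. Neither document says so. The risk lies in how a flat or rising rate would be read against the stated purpose. The primary endpoint, a returned kit, is unaffected, and no change in sample size follows.

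**What to change.** 1. In Section 13(a), replace the stated purpose with whether access at six months differs between home-visit and mailed delivery.
2. In the SAP, add a between-arm comparison of the three binary items at six months. Keep all provider visits in this main analysis, because navigated visits are part of the effect of delivery mode.
3. Label the paired intake-to-exit McNemar results descriptive, with no causal reading about self-sampling.
4. As a descriptive supplement beside endpoint (c), report by arm how many provider visits were study-navigated, where CHW records allow. The documents give CHWs the navigation role but describe no log of attended visits, so this may not be fully obtainable. A version that excludes these visits should not be the main result.

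The cost is one small extra analysis, a wording change in two documents, and giving up a claim about self-sampling and access that the design cannot support. The SAP is written in the past tense; if the analysis is already done, the same changes can be made in the reporting.
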